2.2 Study Treatment

Eligible subjects will be randomly assigned in a 2:1:1 ratio to the following open-label study treatment arms, respectively:

Experimental arm: cabozantinib 40 mg oral qd + atezolizumab 1200 mg infusion q3w

Single-agent cabozantinib arm: cabozantinib 60 mg oral qd

Control arm: sorafenib 400 mg oral bid (800 mg daily)

2.2.1 Study Objectives and Endpoints

The primary objective of this study is to evaluate the efficacy of cabozantinib in combination with atezolizumab versus sorafenib in subjects with advanced HCC who have not received previous systemic anticancer therapy. A secondary objective is to evaluate the single-agent activity of cabozantinib compared with sorafenib in this patient population.

This study has two primary efficacy endpoints. The trial will be declared a success if the null hypothesis is rejected for either of these endpoints; rejection of the null hypotheses for both endpoints is not required.

2.2.2 Primary Efficacy Endpoints

The two primary efficacy endpoints are:

- Duration of progression-free survival (PFS) per Response Evaluation Criteria in Solid Tumors version 1.1 (RECIST 1.1) (Eisenhauer, 2009) by Blinded Independent Review Committee (BIRC) (see Section 7.4.1) for the experimental arm (cabozantinib + atezolizumab) vs. the control arm (sorafenib)
- Duration of overall survival (OS) for the experimental arm (cabozantinib + atezolizumab) vs. the control arm (sorafenib)

2.2.3 Secondary Efficacy Endpoints

- PFS per RECIST 1.1 by BIRC for the single-agent cabozantinib arm vs. the control arm (sorafenib)

2.2.4 Additional Endpoints

- ORR, TTP, and DOR per RECIST 1.1 by BIRC and Investigator
- Evaluation of radiographic response per modified RECIST (mRECIST)
- Safety through the evaluation of AEs, including immune-related adverse events (irAEs) and other AEs of special interest (AESIs).
- Characterization of the pharmacokinetics (PK) of cabozantinib in subjects with previously untreated HCC
- Immunogenicity of atezolizumab given in combination with cabozantinib
- Change in serum AFP from baseline
- Correlation of biomarker analyses with clinical outcomes
- Health-related quality of life (HRQOL) as assessed by the EuroQol Health questionnaire instruments (EQ-5D-5L)
- Health care resource utilization

2.3 Power and Sample Size Justification

The study is designed to provide adequate power for analyses of both primary endpoints of PFS and OS comparing the experimental arm (cabozantinib + atezolizumab) with the control arm (sorafenib), and for the analysis of the secondary endpoint of PFS comparing single-agent cabozantinib with the control arm. For the primary endpoints, a larger sample size is needed to provide reasonable power for OS than is required to evaluate PFS. As a result, if PFS were to be evaluated in the entire study sample, the PFS events may be biased toward shorter progression times. Thus, to allow longer, more robust PFS follow up among a smaller number of subjects, this study employs a “trial within a trial design” (Hessel C, 2016).

Per protocol amendment 2, the total sample size was 740 subjects, to be randomized in a 2:1:1 fashion: 370 to the experimental combination arm (cabozantinib + atezolizumab), 185 to the control arm (sorafenib), and 185 to the single-agent cabozantinib arm.

Per addendum to the protocol amendment 2, the sample size for the global study was increased to ensure the enrollment of at least 185 subjects in the single agent cabozantinib arm in order to allow for enrollment of the protocol-specified number of subjects in this arm. The analyses are to be carried upon observance of the specified number of events as stated in the protocol.

For PFS, a total of 257 events in the first 372 subjects randomized in a 2:1 ratio in the experimental and control arms (n=248 and 124 respectively; the PITT population) provide the study with 90% power for a 2-sided log-rank test with a 1% level of significance to detect a hypothesized true HR of 0.6. Assuming an exponential distribution of PFS, this corresponds with a 67% increase in median PFS from 3.6 months to 6.0 months. The minimum observed effect that would result in statistical significance for PFS is an HR of 0.71, a 41% improvement in median from 3.6 to 5.1 months. Interim analysis of PFS is not planned.

For OS, a total of 368 deaths among all 555 subjects randomized in a 2:1 ratio in the experimental (n=370) and control arms (n=185) are required to provide 90% power to detect an HR of 0.69 using the log-rank test and a 2-sided significance level of 4%. Assuming an exponential distribution for OS, this corresponds to a 45% increase in median survival from 12.3 months to 17.8 months. The minimum observed effect that would result in statistical significance for the primary analysis of OS is an HR of 0.7942, a 26% improvement in median from 12.3 to 15.5 months.

For the secondary endpoint of PFS, a total of 283 events among all 370 subjects (185 per arm) in the single-agent cabozantinib and control arms provides the study with 85% power for a 2-sided log-rank test with a 1% level of significance to detect a hypothesized true HR of 0.65. Assuming an exponential distribution for PFS, this corresponds with a 53% increase in median PFS from 3.6 months to 5.5 months. The minimum observed effect that would result in statistical significance for PFS is an HR of 0.736, a 36% improvement in median from 3.6 to 4.9 months.

With an average accrual rate of 30 subjects per month it is estimated that it will take approximately 18.4 months to observe the required primary PFS events (16.5 months of subject accrual) and approximately 38 months to observe the required deaths for OS (25 months of subject accrual) to evaluate the primary endpoints in the combination and control arms. Assuming the same accrual rate, it is anticipated that it will take approximately 25 months to observe the required secondary PFS events (25 months of subject accrual) to evaluate the secondary endpoint in the single-agent cabozantinib and control arms. These estimates are based upon the statistical assumptions, adjusted to accommodate the time required for all study sites to be activated and for subject recruitment to reach full potential. The true intervals required to meet these milestones may be longer or shorter due to divergence from assumptions, including non-constant accrual rate due to the time required for all study sites to become active. The sample size was increased to up to 837 subjects to ensure the needed enrollment of at least 185 subjects in the single-agent cabozantinib arm.

An overview of the endpoints and operating characteristics is shown in Table 3:

Table 3: Summary of Endpoint Operating Characteristics

Accrual per month	30 subjects		
Randomization allocation	2:1 within Experimental and Control Arms		1:1 within Single-Agent Cabozantinib and Control Arms
Endpoint:	PFS: Primary endpoint	OS: Primary endpoint	PFS: Secondary endpoint
Power	90%	90%	85%
Alpha allocated (2-sided)	0.01	0.04	0.01
# of interim analyses (approximate information fraction)	0 (NA)	2 (33%, 66%)	1 (67%)
Assumed median, control (months)	3.6	12.3	3.6
Assumed median, experimental (months)	6.0	17.8	5.5
Assumed HR	0.60	0.69	0.65
Number of events	257	368	283
N for analysis	372	555	370
Population	PITT Population	ITT Population	ITT Population
Planned n1 vs n2	248 vs 124	370 vs 185	185 vs 185
Time to enroll (months)	16.5	25	25
Time to trigger event (months)	18.4	38	25

Power and sample size estimates were calculated using EAST v6.5 by Cytel Software.

2.4 Randomization and Blinding

This is a multicenter, randomized, open-label controlled Phase 3 study. The study treatment assignment will be known to the subjects, investigators, study centers, Sponsor, and any Contract Research Organization affiliated with the study other than the BIRC. Study staff supporting the BIRC will ensure that the blind is maintained for the BIRC.

After obtaining informed consent, the site representative will use the designated web-based interactive response technology (IRT) system to register a subject for screening. The IRT will assign a unique subject number. When a subject has been deemed eligible at the study site, the site representative will use the IRT to randomize the subject into the study.

Eligible subjects will be randomly assigned in a 2:1:1 ratio to the three study treatment arms. (See Section 2.2):

Stratified randomization will be conducted using permuted blocks over 12 strata. The 12 strata are based on all combinations of the following 3 stratification factors which will be established at screening:

- Disease etiology (HBV [with or without hepatitis C virus {HCV}], HCV [without HBV], or Other)
- Region (Asia, Other)
- Presence of extrahepatic disease and/or macrovascular invasion (Yes, No)

Protocol amendment 1 necessitated the sample size of the single-agent cabozantinib arm to be increased to support the comparison of the single-agent cabozantinib arm with the sorafenib (control) arm. As a consequence, the original allocation ratio of 6:3:1 of the experimental arm, control arm and the single-agent cabozantinib arm was changed to 2:1:1 in the respective arms in the amendment. The subjects enrolled under the original protocol will have the initial allocation ratio of 6:3:1.

3 ANALYSIS POPULATIONS

The planned analysis populations are briefly summarized in Table 4. The populations specified below pertain to the global study population and do not include the subjects enrolled in the China Extension Phase. The addendum to Protocol amendment 2 allowed for the global enrollment (excluding the China Extension Phase) to be up to 840 subjects to ensure enrollment of at least 185 subjects in the single agent cabozantinib arm. The study enrolled 188 subjects in the single agent cabozantinib arm in the global study population. The 188th subject randomized to the single agent cabozantinib arm was considered the last subject in the global study population of 837 subjects. Subjects randomized in China after this date are in the China Extension Phase only. Analyses that include the China Extension Phase are beyond the scope of this plan. Further information on the global study population is provided in the sections below.

Table 4: Analysis Populations for the Global Study Population

Analysis	Population	Subjects
Primary PFS	PITT	First 372 subjects randomized to experimental or control arms
Primary OS	ITT	All subjects randomized to experimental or control arms
Secondary PFS	ITT	All subjects randomized in control and single-agent cabozantinib arms
Additional efficacy analyses	ITT	All randomized subjects in the three treatment arms
Safety analyses	Safety	All subjects who received any study treatment
Safety analyses for PITT subjects	P-Safety	All subjects who received any study treatment in the PITT population

All populations exclude the China Extension Phase.

ITT, Intent-to-Treat; OS, overall survival; PFS, progression-free survival; PITT, PFS Intent-to-Treat; P-Safety, PFS Safety

3.1 Intent to Treat Population

The ITT population will consist of all subjects who are randomized to any of the three study treatment arms (the experimental arm [cabozantinib + atezolizumab], the single-agent cabozantinib arm, or the control arm [sorafenib]), regardless of whether any study treatment or the correct study treatment was received.

3.2 PFS Intent to Treat Population

The first 372 subjects randomized (based upon Greenwich Mean Time randomization date/time values) to the experimental (cabozantinib + atezolizumab) arm and control (sorafenib) arm will be considered as the PFS Intent-to Treat (PITT) population. This population will be used for the analysis of the primary endpoint. The population may be extended to the first 410 subjects randomized to the two groups if a review of the accumulating events required will not be reached (due to censoring) among the first 372 subjects originally planned.

3.3 Safety Population

The Safety population will consist of all subjects who receive any amount of study treatment. Analyses based on Safety population will be performed according to the actual treatment received for the length of the study. For example, a subject randomized to the sorafenib arm who received cabozantinib + atezolizumab in error, and only received the combination regimen, would be analyzed in the combination arm for safety summaries. Subjects who receive treatment components from both the cabozantinib + atezolizumab and sorafenib arm in error (e.g. received sorafenib and either cabozantinib and/or atezolizumab) will be excluded from the safety population. Their safety data will be presented in by-subject listings.

3.4 PFS Safety Population

The PFS Safety (P-Safety) population will include the subjects included in the PITT population receiving any amount of study treatment.

3.5 Per Protocol Population

A Per Protocol population is not defined or planned for the study.

4 GENERAL CONVENTIONS

The statistical principles applied in the design and planned analyses of this study are consistent with International Conference on Harmonization (ICH) E9 (ICH Harmonized Guideline E9 Statistical Principles for Clinical Trials, 1998) and draft E9 R1 guidelines (ICH Harmonized Guideline E9 (R1) Statistical Principles for Clinical Trials: Addendum: Estimands and Sensitivity Analysis in Clinical Trials (Draft), 2017).

Continuous data will be summarized using descriptive statistics (number of observations, mean, standard deviation, median, 25th and 75th percentiles, minimum, and maximum). Frequencies and percentages will be used for summarizing categorical (discrete) data.

Confidence intervals, when presented, will generally be constructed at the 95% level. For binomial variables, the Clopper-Pearson method (Clopper CJ, 1934) may be employed unless otherwise specified.

A month is operationally defined to be 30.4375 days. Six months is operationally defined to be 183 days.

Efficacy summaries will be presented by treatment arm randomized to and safety summaries by treatment received unless otherwise specified.

4.1 Treatment Periods, Summary Groups, Analyses, and Reports

For each subject, data collected for this study will be grouped by the following two treatment periods in which it was obtained:

Core Period: This period begins with screening. The end of this period is the earlier of the data cutoff date (for a particular analysis), date of withdrawal from study, date of discontinuation from or loss to survival follow-up, date of death, date of initiation of the Maintenance Phase or date of enrollment to the Crossover Phase -1.

Crossover Period: The start of this period is the enrollment date of the Crossover Phase, and it ends at the earlier of date of withdrawal from study, date of discontinuation from study treatment or loss to survival follow-up, date of death, or date the Maintenance Phase is initiated.

The following sets of summaries are planned:

- Primary safety and efficacy summaries for the clinical study report (CSR) and any CSR addendums in support of primary efficacy endpoint analyses will include all and only data obtained in the Core Period and presented separately as follows:
 - cabozantinib + atezolizumab versus sorafenib
 - single-agent cabozantinib versus sorafenib

Table 5: Schema for Efficacy Summaries

Treatment Period	Core Period (Summaries provided in primary CSR and efficacy addendum(s))		
Population	Subjects randomized to cabo+atezo (Experimental Arm)	Subjects randomized to single-agent cabozantinib (Single-agent arm)	Subjects randomized to sorafenib (Control arm)
Start Date of Period	Randomization date	Randomization date	Randomization date

- Upon completion of all study data collection, only safety summaries will be repeated for the final CSR safety addendum and will include data from the Crossover period and updated data from the Core period

Table 6: Schema for Safety Summaries

Treatment Period	Core Period (Summaries provided in primary CSR and updated in CSR safety addendums)			Crossover Period (Summaries provided in final CSR safety addendum only)
Population	Subjects randomized to and who received cabozantinib+atezolizumab (Experimental Arm)	Subjects randomized to and who received single-agent cabozantinib (Single-agent Arm)	Subjects randomized to and who received sorafenib (Control arm)	sorafenib or single agent cabozantinib subjects who cross over to receive cabozantinib+atezolizumab (Crossover subjects)
Start Date of Period	Date of 1 st dose of cabo and/or atezo	Date of 1 st dose of cabozantinib	Date of 1 st dose of sorafenib	Date of 1 st dose of cabo+atezo

Up to six study analyses are planned over the course of the study:

1. Primary PFS + interim OS #1 + interim secondary PFS [Core treatment period]
2. Interim OS #2, if interim OS #1 is not successful [Core treatment period]
3. Final OS, if interim OS #1 and #2 are not successful [Core treatment period]
4. Final secondary PFS analysis [Core treatment period]
5. Safety update for 90-day report [Core treatment period]
6. Final safety update, upon initiation of the Maintenance Phase [Core and Crossover treatment periods]

Some of the analyses listed above may be contemporaneous depending on the occurrence of the events. Details on the interim analyses of OS, secondary PFS and the control of type 1 error are provided in Sections 7.2 and 7.3.

4.2 Definition of Baseline

In general, for efficacy endpoints the last observed measurement prior to randomization will be considered the baseline measurement.

For safety endpoints the last observation before first dose of study treatment will be considered the baseline measurement unless otherwise specified and will be established for each period defined in Section 4.6.

For assessments on the day of first dose of study treatment where time is not captured, if such procedures are required by the protocol to be conducted before first dose or a nominal pre-dose indicator is available, this will serve as sufficient evidence that the assessment occurred prior to first dose.

For the experimental arm (cabozantinib + atezolizumab treatment), the earliest instance of administration of either cabozantinib or atezolizumab on the study will be considered as the time point of first dose. Similarly, the latest instance of administration of either of the treatments will be considered as the time point of last dose.

4.3 Definition of Study Day

For the purpose of efficacy data summaries which are based only on data collected in the Core period, Study Day is defined with respect to the randomization date. For visits (or events) that occur on or after randomization, study day is defined as (date of visit [event] – date of randomization + 1). For visits (or events) that occur prior to randomization, study day is defined as (date of visit [event] – date of randomization). There is no Study Day 0.

For the purpose of safety data summaries, Dose Day is defined with respect to the date of first dose of study treatment received in the respective periods defined in Section 4.6. For visits (or events) that occur on or after first dose, dose day is defined as (date of visit [event] – date of first dose of study treatment + 1). For visits (or events) that occur prior to first dose, dose day is defined as (date of visit [event] – date of first dose of study treatment). There is no Dose Day 0.

The last dose date for each individual agent and for any study treatment is defined for each of the periods described in Section 4.1. For listings (such as for adverse events [AEs]) that include the derivations of “days since last dose,” this is defined for each agent as (event date – date of last dose for the agent). Two such fields, one for cabozantinib and one for atezolizumab will be presented for subjects receiving the combination of these agents. Events that occur on the same day as the last dose of a particular study drug will therefore be described as occurring zero days from the last dose of that study drug.

4.4 Visit Window Calculation

Analyses will be according to actual visit dates and times. The planned analyses do not require the calculation of visit windows. However, for analyses that require a particular visit as planned, measurements included in that visit must have occurred during the acceptable window defined for the visit in the protocol, unless otherwise specified in this plan.

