Required safety assessments are to be performed on a schedule based on the date of the first dose (W1D1) and every 3 weeks (\pm 3 days) (ie, W4D1, W7D1, W10D1, etc). For subjects in the combination arm, required safety assessments may occur outside the protocol-defined windows due to safety-driven delays in atezolizumab administration and will not be considered protocol deviations as long as required safety assessments are performed at least every 3 weeks (\pm 3 days). See the CRF completion guidelines for instructions on how to enter study data in such circumstances. The following are the reminders:

- Doses of atezolizumab must not be given less than 19 days apart (see [Section 6.2.4](#)).
- Specific laboratory tests are required to be performed and evaluated within 72 hours prior to each administration of atezolizumab (see [Section 5.8.5](#)).
- The tumor assessment and HRQOL schedules are to be maintained relative to the date of first dose of study treatment (or randomization date for subjects never treated) irrespective of the dates of safety assessments.
- PK and biomarker sample collection schedules are per schedule of assessments ([Appendix A](#) and [Appendix B](#)).

Safety follow-up visits will be performed 30 (+14) days (FU-1) and approximately 100 days (\pm 14 days) (FU-2) after the date of the decision to permanently discontinue study treatment (see [Section 8.4](#)).

If study treatment is held due to AEs, investigators should perform additional safety assessments weekly (or more frequently as clinically indicated).

Radiographic tumor assessments should be performed as described in [Section 5.8.6](#), and HRQOL assessments should be performed as described in [Section 5.8.8](#). The schedule of assessments should be maintained regardless of whether study treatment is given, reduced, held or discontinued until a criterion for discontinuation of radiographic assessments is met (see [Section 5.8.6.2](#)).

In accordance with the ITT principle, HRQOL, radiographic tumor assessments, and survival follow-up are to be performed per protocol even for subjects randomized who never receive study treatment. For such subjects, W1D1 is defined as the date of randomization.

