Appendix A: Schedule of Assessments

The schedule of required assessments is presented in this appendix. Following randomization, assessments for safety and patient reported outcomes are to occur corresponding with study weeks (eg, Week 5 Day 1 [W5D1]) which are fixed from Week 1 Day 1 (W1D1) defined as the date of the first dose of study treatment. W1D1 should occur within 3 days after randomization. All assessments for radiographic endpoints (CT, MRI) as well as HRQOL (ie, EQ-5D-5L) will be scheduled based on W1D1 and are to be performed even for subjects randomized but never treated. For such subjects, W1D1 is defined as the date of randomization.

In the absence of toxicity, all scheduled safety visits should occur within \pm 3 days of the nominal visit day, unless otherwise indicated. For subjects in the combination arm, required safety assessments may occur outside the protocol defined windows due to safety-driven delays in atezolizumab administration and will not be considered protocol deviations as long as required safety assessments are performed at least every 3 weeks (\pm 3 days). See the CRF completion guidelines for instructions on how to enter study data in such circumstances.

If study treatment is held or missed after W1D1, assessments should continue following the schedule described below.

Unscheduled safety assessments or phone calls, if required as defined in the protocol, are to be performed weekly (or more frequently) as clinically indicated. See [Section 5.7](#) for further details.

Special accommodations during the global COVID-19 pandemic are described in [Appendix M](#).

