^e Serum chemistry, hematology, coagulation, and urinalysis laboratory samples must be collected, and results must be reviewed within 72 hours before any atezolizumab infusion administered on study. If the subject has symptoms indicative of a thyroid function disorder, thyroid function test results are to be reviewed prior to

administering atezolizumab. See [Section 5.8.5](#) and the Laboratory Manual for more detailed information on laboratory assessments and when local assessments may be performed in lieu of central assessments for serum chemistry, hematology, coagulation, and thyroid function prior to atezolizumab administration.

^f For women under the age of 55 years to confirm menopause as needed.

^g Archival tumor tissue (most recently obtained) will be provided, if available. If archival tissue and histological/cytological confirmation of disease are not available, a tumor biopsy may be collected during screening with subject consent

^h HRQOL forms should be administered and collected prior to any other study-related activities for scheduled visits. Questionnaires should be completed prior to the clinic visit or if completed on the day of the visit prior to seeing the study site personnel.

ⁱ For each on-treatment visit, the PK sample should be collected approximately 8 or more hours after the previous dose of cabozantinib, and if cabozantinib will be administered on that day, should be collected prior to cabozantinib administration. The investigator will ask the subject for the date and time of the most recent prior dose of cabozantinib and this information will be recorded on the appropriate CRF page.

^j Clinical diagnosis of HCC by multiphase imaging using CT or MRI in subjects with cirrhosis for eligibility may be performed at the sites accredited by the Sponsor. Diagnostic scans may be used for screening if they meet the criteria described in [Section 5.8.6.2](#). Refer to the guidance on diagnosis of HCC in cirrhotic patients by imaging in [Section 5.8.6.1](#).

^k For subjects in the combination arm, required safety assessments may occur outside the protocol defined windows due to safety-driven delays in atezolizumab administration and will not be considered protocol deviations as long as required safety assessments are performed at least every 3 weeks (\pm 3 days). See the CRF completion guidelines for instructions on how to enter study data in such circumstances

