7.5.8 Serum Alpha-Fetoprotein (AFP)

Serum AFP is assessed in the study at various time points such as baseline, W4D1, W7D1, W10D1, W13D1, FU1, and FU2. Serum AFP will be analyzed as a continuous and discrete variable (<400 ng/mL, ≥ 400 ng/mL) to assess its potential as a prognostic marker. The serum levels and change from baseline (absolute and percent change) will be summarized using descriptive statistics at various measurement time points and presented by study treatment arm for both PITT and ITT populations. Descriptive statistics for best/worst percent change since baseline will also be presented per arm using all available data at protocol-defined time points.

Best change is defined as the largest reduction (or smallest increase if no reduction) and worst change is defined as the largest increase (or smallest reduction if no increase).

Appropriate transformations may be applied to normalize the data for presentation or analysis. AFP may also be categorized based on previously published measures. For example, a decrease from baseline of 20% or more in serum AFP by or at a specific time point (say, W7D1) may be defined post-hoc as a prognostic response.

Exploratory modeling analyses including survival analyses with time dependent covariates, general linear models, and mixed models with repeated measures will be employed to assess meaningful relationships between AFP levels or changes from baseline and clinical outcomes.

A waterfall plot of best percentage change (i.e., best percentage decrease) from baseline in AFP will be presented for each treatment group using the PITT and ITT populations. In all calculations, best change from baseline will be based only on protocol-defined time-points.

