8.4.2 Analysis

All laboratory data parameters and visits will include flags for values above or below laboratory reference ranges. Toxicity grades will be assigned programmatically by applying the CTCAE v 5

guidelines. Only results with assessment dates through the end of the safety observation period (see Section 4.6) will be tabulated in summary tables.

Laboratory summaries will be presented in SI units. Continuous laboratory test results will be summarized by treatment group using descriptive statistics for actual values and for changes from baseline by scheduled visit. For test results which are below or above the quantification level, the imputed values as described in Appendix C will be used for deriving the grade and then summarized. Box-Whiskers plots may also be presented at each scheduled visit (with visits shown on x-axis) for some laboratory parameters for IDMC review purposes. Line graphs for mean change from baseline \pm standard deviation will also be presented at each scheduled visit (with visits shown on x-axis) for the following laboratory parameters.

- Renal function
 - Blood urea nitrogen (BUN)
 - Creatinine
- Liver function panel
 - Total bilirubin
 - ALT
 - AST

Tables summarizing baseline laboratory values and the incidence of laboratory abnormalities by baseline and maximum post-baseline CTCAE grade over all records will be presented. In addition, the following summaries will also be presented:

- A. Liver function abnormalities will be assessed as follows:
 - Shift from baseline based on normal ranges
 - Summaries of subjects meeting Hy's Law laboratory screening criteria as shown below:
 - $> 3 \times$ ULN (ALT or AST), $> 2 \times$ ULN Total Bilirubin, and $< 2 \times$ ULN ALP
 - $> 3 \times$ ULN (ALT or AST), $> 2 \times$ ULN Total Bilirubin, and $\geq 2 \times$ ULN ALP
 - $> 3 \times$ ULN (ALT or AST), $> 2 \times$ ULN Total Bilirubin
- B. For renal failure surveillance, a summary of subjects meeting renal failure laboratory screening criteria as shown below will be provided:
 - Serum creatinine $\geq 3.0 \times$ ULN and $\geq 2.0 \times$ baseline value or
 - Estimated Glomerular Filtration Rate (eGFR) $\leq 50\%$ of the baseline value or
 - eGFR < 30 mL/min/1.73 m² and $\geq 25\%$ reduction from the baseline value

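### Read literally, the in-window rule in SAP 4.4 discards protocol-permitted late combination-arm results from the by-visit laboratory and AFP summaries

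*SAP*

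**What the plan says.** SAP 4.4 makes actual dates the default and states: "The planned analyses do not require the calculation of visit windows". It then makes an exception. Where an analysis needs a particular planned visit, "measurements included in that visit must have occurred during the acceptable window defined for the visit in the protocol", unless the SAP specifies otherwise.

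Two SAP sections produce summaries by planned visit:
- SAP 8.4.2 summarises laboratory tests "using descriptive statistics for actual values and for changes from baseline by scheduled visit" and adds line graphs of mean change by scheduled visit for BUN, creatinine, total bilirubin, ALT and AST.
- SAP 7.5.8 says AFP levels and changes "will be summarized using descriptive statistics at various measurement time points", naming W4D1, W7D1, W10D1, W13D1 and the two follow-up visits. It limits best and worst change to protocol-defined time points.

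Neither section sets a different visit rule, and SAP 4.5 does not impute missing values.

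The protocol treats timing differently. Appendix A says: "In the absence of toxicity, all scheduled safety visits should occur within" ±3 days of the nominal day. Protocol 5.2 then allows that, in the combination arm, "required safety assessments may occur outside the protocol-defined windows due to safety-driven delays in atezolizumab administration", and that this is not a deviation provided assessments are still done at least every 3 weeks (±3 days). Footnote k of the Appendix A schedule repeats the allowance and is attached to the AFP, hematology, chemistry, coagulation and urine rows. No equivalent allowance is written for the sorafenib or single-agent cabozantinib arms.

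**The concern.** The two documents do not fit together. A late combination-arm result that the protocol accepts as compliant is, under the SAP's stated rule, not admissible to its visit. The reason for lateness is a safety-driven infusion delay, so the values lost would come from subjects with toxicity, in the one arm with an explicit allowance.

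The outputs at stake are the by-visit mean-change tables and graphs for renal and liver function, and the AFP change summaries. Protocol 6.6.2.4 expects hepatobiliary adverse events to be relatively frequent in this population, so the liver plots will be read closely. A by-visit mean that loses values after a toxicity-related delay in one arm could look more favourable than the full data.

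**Working it through.** There is no figure in the plan to reproduce. The check sets the timing rules side by side and enumerates which visits survive.

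**Inputs**
- Nominal days, counting W1D1 as day 1: W4D1 = 22, W7D1 = 43, W10D1 = 64, W13D1 = 85 (21-day spacing, protocol 5.2 and Appendix A).
- Window ±3 days (Appendix A), giving 19–25, 40–46, 61–67 and 82–88.
- Assumption: the infusion and its assessments are delayed by d days at W7 and then continue every 21 days from the delayed date. Assessment days are then 22, 43 + d, 64 + d, 85 + d.

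**Which visits have an in-window value**

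| Delay d (days) | W7, W10, W13 days | Visits lost through W13 |
|---|---|---|
| 0–3 | up to 46, 67, 88 | none |
| 4 | 47, 68, 89 | W7, W10, W13 |
| 17 | 60, 81, 102 | W7, W10, W13 |
| 18–24 | 61–67, 82–88, later | W7 only; the moved results fall into the W10 and W13 windows |
| 25–28 | 68–71, 89–92, later | W7, W10, W13 again |

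The 4–17 day band follows from the spacing. A shift of more than 3 days leaves a visit's own window, and a shift below 21 − 3 = 18 days has not reached the next one. In that band 3 of the 4 on-treatment points through W13 are lost.

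**Adding the protocol's 3-weekly condition.** The gap from W4 to the delayed W7 assessment is 21 + d days, which exceeds 24 once d > 3. Staying within the allowance therefore implies an extra assessment in between. If that is an on-schedule W7 assessment at day 43, W7 is kept, but W10 and W13 are still lost for d = 4 to 17. Adding weekly assessments during the hold does not change this for those delays.

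**If only the infusion moves** and assessments stay at days 22, 43, 64 and 85, nothing is lost.

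**Would assessments move?** Protocol 5.8.5 requires chemistry, hematology, coagulation and urinalysis within 72 hours before each atezolizumab dose, so a delayed infusion needs tests near the delayed date.

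**How often?** The only delay rate in the documents is protocol Table 1, from the Phase 1b dose escalation: 1 of 6 subjects at cabozantinib 40 mg (17%), exact 95% CI 0.4% to 64%. As an assumption only, any-delay rates of 5%, 10%, 17% and 30% among 370 planned combination subjects give about 19, 37, 62 and 111 subjects. These are upper limits at each assumed rate, because only delays that carry assessments out of window cost any value.

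**The case against.** The strongest reply is that the plan need not lose anything:

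- SAP 4.4 defaults to actual dates and restricts only analyses that need a planned visit. It does not say that the laboratory and AFP tables are in that class. That is fair, but a table by scheduled visit is hard to place anywhere else.
- Appendix A says assessments continue on schedule when treatment is held or missed, and that infusion days need not coincide with safety visits. Protocol 5.2 adds weekly checks during holds. This stands: a site that keeps the fixed schedule loses no values. It does not settle the matter, because the same protocol expressly allows assessments to leave the window. Change-from-baseline summaries also use central-laboratory results only (SAP 8.4.2), while tests needed quickly may be local (protocol 5.7 and 5.8.5). The SAP does not say whether an unscheduled result can fill a scheduled visit.
- The protocol refers to CRF completion guidelines for entering such data, which are not available here. A visit label alone would not rescue a value, since SAP 4.4 tests the date against the protocol window.
- The Appendix A wording about absence of toxicity covers all arms, so some toxicity-related lateness may occur elsewhere too. This also stands. Only the explicit infusion-delay allowance is confined to the combination arm.

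Two stronger readings are tempting. A reader might infer that subjects with toxicity vanish from the combination-arm tables. They do not: in-window values before the delay stay, and only individual visit values are at risk. A reader might also take 7 of the 8 visits from W4 to W25 as lost and multiply by the Phase 1b rates: 7/8 × 1/6 ≈ 15% and 7/8 × 4/6 ≈ 58% of records. The documents do not support that range. It needs every delay to start at W7, exceed 3 days and never realign. The 4/6 comes from the 60 mg cohort, whereas this arm starts at 40 mg. Both rates rest on six subjects with renal cell carcinoma. AFP is not scheduled between W13 and follow-up.

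**Conclusion.** The inconsistency holds and is minor. Applied literally, SAP 4.4 removes protocol-compliant combination-arm laboratory and AFP values from by-visit summaries when assessments move with a delayed infusion by about 4 to 17 days and then continue every 21 days. A delay of 18 to 24 days costs only the delayed visit, and keeping the fixed schedule costs nothing. Any loss is triggered by toxicity, tied to an allowance written for one arm only, and not imputed. Its size cannot be stated, because it depends on site practice and on a delay rate that the documents do not give for this trial.

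The limits are clear. Incidence, shift and worst-grade laboratory tables use all available results (SAP 8.4.2). The affected outputs are descriptive or exploratory. No primary or secondary test, alpha level or sample size is touched. Vital signs are not affected, because SAP 8.5.2 has no by-visit vital-sign table.

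**What to change.** For by-visit laboratory and AFP summaries, replace the last sentence of SAP 4.4 with contiguous analysis windows, applied identically in all arms:
- Assign each post-baseline result, including unscheduled central-laboratory results, to the scheduled visit with the nearest nominal day.
- If several results fall to one visit, use the closest.
- Keep ±3 days only as a check for deviations.
- Show the number of subjects contributing at each visit in each arm, so that any remaining imbalance is visible.

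The cost is SAP wording and one derived visit variable. No new data are needed.
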